--	--

	
following:
 
 • Respiratory Severity Score (RSS) ≥ 2.4 • Partial Pressure of Carbon Dioxide (PCO_2) $> 65 \text{ mg Hg}$ and/or $\text{pH} < 7.20$ • Base deficit $> 10 \text{ mEq/L}$, on two blood gases 4 hours apart • nCPAP $> 8 \text{ cm}$ • Three severe apneas with bradycardia within six hours requiring escalation of support • Infant's work of breathing has increased warranting escalating therapy, but infant does not meet RSS or other criteria above. 
Study treatment will be discontinued if any of the following occur:
 
 1. Pneumothorax (requiring chest tube) 2. Pulmonary hemorrhage (frank bleeding from the lungs that is not related to irritation due to suctioning or infection) 3. Infant shows evidence of pulmonary hypertension requiring iNO 
Each infant will be clinically assessed and evaluated per protocol during their stay in the NICU, to 40 weeks PMA or discharge, whichever comes first.

	
Part II
 
Patients who survive to 40 weeks PMA or discharge will be eligible for Part II. Part II will begin at discharge/40 weeks PMA and include telephone Questionnaires performed at 3, 6, 9 and 12 months corrected age . Evaluation of home environment, respiratory support, medical history, modified GMFS and respiratory resource utilization after discharge will be collected. (See Appendices for Questionnaires)

Number/Type of Subjects	Approximately 261 (87 per study arm) subjects will be block randomized in a 1:1:1 allocation. This number will be reassessed at the interim analysis.
Inclusion Criteria	
Preterm infants are eligible for this study if they meet all of the following criteria:
 
 1. Parental consent obtained prior to study procedures being performed (pre-natal consent is allowed) 2. 26 0/7 to 31 6/7 weeks of gestational age 3. Weight $< 2000 \text{ grams}$ 4. Weight appropriate for gestational age (AGA 3% to 97%) 5. Age \leq twenty-four hours at the initiation of study treatment 6. RSS ($\text{MAP} \times \text{FiO}_2$) $1.4 - 2.0$ on nCPAP or nIMV 7. Chest radiograph or lung ultrasound [13,14] consistent with a diagnosis of RDS

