13.2.8	Handling of Study Investigational Product	57
13.2.9	Publication of Results	57
13.2.10	Disclosure and Confidentiality	57
13.2.11	Discontinuation of Study	57
13.2.12	Patient Insurance and Indemnity	58
14	REFERENCES	59
15	APPENDIX I- PART I DISCHARGE BREATHING QUESTIONNAIRE	61
16	APPENDIX II – PART II QUESTIONNAIRE.....	63

LIST OF ACRONYMS, ABBREVIATIONS AND DEFINITION OF TERMS

Abbreviation	Term
AE	Adverse Event
AF	AeroFact
AGA	Appropriate for Gestational Age
APC	Aerogen Pharma Corporation
BiPAP	Bilevel Positive Airway Pressure
BP	Blood Pressure
BPD	Bronchopulmonary Dysplasia
CFR	Code of Federal Regulations
CLN	Clinical
CMV	Continuous Mandatory Ventilation
Corrected Age	Chronological Age - Weeks Premature
CPAP	Continuous Positive Airway Pressure
CRA	Clinical Research Associate
CRF	Case Report Form
CRO	Contract Research Organization
CSR	Clinical Study Report
CV	Coefficient of Variation
Cystic PVL	Cystic Periventricular Leukomalacia
DSMB	Data Safety Monitoring Board
ETT	Endotracheal Tube
FDA	Food and Drug Administration
FiO ₂	Fraction of Inspired Oxygen
GCP	Good Clinical Practice
GMFS	Gross Motor Function Score (Modified)
HFJV	High Frequency Jet Ventilation
HFNC	High Flow Nasal Cannula
HFOV	High Frequency Oscillatory Ventilation
HR	Heart Rate
IB	Investigator's Brochure
ICF	Informed Consent Form
ICH	International Conference on Harmonization
IEC	Independent Ethics Committee
ITT	Intention to Treat
IRB	Institutional Review Board
IVH	Intraventricular Hemorrhage
IP	Investigational Product
kg	Kilogram
LOS	Length of Stay
MAP	Mean airway pressure

Abbreviation	Term
MedDRA	Medical Dictionary for Regulatory Activities
mg	milligram
min	Minute
MOP	Manual of Procedures
NC	Nasal Cannula
nCPAP	Nasal Continuous Positive Airway Pressure
NEC	Necrotizing Enterocolitis
NICU	Neonatal Intensive Care Unit
NIH	National Institutes of Health
nIMV	Nasal Intermittent Mandatory Ventilation
O ₂	Oxygen
OTC	Over-the-Counter
PCO ₂	Partial Pressure of Carbon Dioxide
PO ₂	Partial Pressure of Oxygen
Paw	Mean Airway Pressure
PDA	Patent Ductus Arteriosus
PEEP	Positive-End Expiratory Pressure
PHT	Pulmonary Hypertension
PIE	Pulmonary Interstitial Emphysema
PIP	Peak Inspiratory Pressure
PMA	Postmenstrual Age
PPP	Per Protocol Population
PPHN	Persistent Pulmonary Hypertension in the Neonate
PROM	Premature Rupture of Membranes
RAC	Room Air Challenge
RDS	Respiratory Distress Syndrome
Respiration Sensor	aka Breath Sensor
ROP	Retinopathy of Prematurity
RR	Respiration Rate

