3.2 Part II – Additional Objectives

- To evaluate pulmonary outcomes and respiratory resource utilization at 3, 6, 9, and 12 months corrected age.
- To evaluate respiratory morbidity per quarter and compare pulmonary morbidity across groups
- To evaluate early neurologic (modified GMFS) outcomes at 12 months corrected age

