7.3 Additional Efficacy Endpoints – Part II

- Assessment of pulmonary outcomes at 3, 6, 9 and 12 months corrected age
- Length of NICU Stay (LOS)
- Proportion of subjects with any respiratory resource utilization at 3, 6, 9 and 12 months corrected age
- Respiratory morbidity per quarter till 12 months corrected age
- Assessment of modified GMFS at 12 months corrected age

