10.2 Part II – Follow-Up

10.2.1 Follow-Up Questionnaires

Follow-Up Questionnaires will be completed by telephone with parents at 3, 6, 9, and 12 months corrected age to assess current respiratory support, the home environment, interim medical history and respiratory medical resource utilization and neurological outcomes (12 months corrected only).

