13.11. Form Signed Yes No

16 APPENDIX II – PART II QUESTIONNAIRE

Part II Follow Up Questions	3 months Corrected Age	6 months Corrected Age	9 months Corrected Age	12 months Corrected Age
Respiratory symptoms	X	X	X	X
Dr visit/ER/hospital visit	X	X	X	X
Oxygen/ventilator use	X	X	X	X
Respiratory Medications	X	X	X	X
Home living situation	X	X	X	X
Type and route of feedings		X		X
Care outside home		X		X
Smoking in home		X		X
Family/social history				X
Medical history, vision hearing				X
Medications for chronic conditions				X
Allergies				X
Motor milestones				X
Growth parameters				X
Modified Gross Motor Function Score				X

AeroFact 2b – Part II – Follow-Up1. Corrected Age at current Interview: 3 Months 6 Months 9 Months 12 MonthsHistory of last interview

2. Date of last interview ____/____/____

2a. Date of NICU Discharge: ____/____/____ N/A

3. Which was last interview conducted:

 Discharge 3 Months 6 Months 9 Months

4. Was the interview conducted for the current period?

 Yes

i. Date of this interview ____/____/____

ii. Where was questionnaire performed?

1. In hospital as in-patient
2. In person at follow-up clinic
3. Over the telephone

 Noi. Reason this interview was not conducted (*select one*)

1. Child died
2. Unable to Contact
3. Family refused this contact

4. Consent withdrawn. No further follow-up
5. Other (Describe): _____

5. Information received from:

 Mother Father Grandparent Foster Parent Other

6. Since discharge (or last interview), has your child had a cough without a cold?
 Yes No

6.a. If Yes, how often do you notice a cough without a cold?

- a. Every day
- b. Not every day, but more than once per week
- c. Once a week
- d. Not every week

6.b. When does your child have this cough without a cold? (select one)

- a. More often during the day
- b. The same amount whether it is day or night
- c. More often at night

7. Since discharge (or last interview), has a medical person (nurse or doctor) told you he/she heard wheezing when listening to your child's chest?

Yes No

7.a. If Yes, when has a medical person heard wheezing in your child's chest? (select one)

- a. Only when my child has a cold
- b. Only when my child has NOT had a cold
- c. Both when my child has a cold and without a cold

8. Since discharge (or last interview), has your child been treated in the Emergency Department or by another doctor in the office or clinic because of a breathing problem or a change in his/her breathing?

Yes No N/A

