8.a. If yes, how many times was your child treated in the Emergency Department, office or clinic?

≤ 2 3-5 6-10 > 10

9. Since discharge (or last interview), has your child been admitted to the hospital overnight?

Yes No N/A

9.a. How many times was your child admitted to the hospital overnight?

9b. How many times was this because of a breathing problem or a change in his/her breathing?

10. Is your child currently on oxygen or a breathing machine (ventilator) at home (or in hospital)?

Yes

10.a. Is child currently on oxygen? Yes No

10.b. Is child currently on a ventilator? Yes No

No

10.c. Has your child been on oxygen at home since discharge (or last interview)? Yes No

10.d. Has your child been on a ventilator at home since discharge (or last interview)? Yes No

11. Since discharge (or last interview), has your child been diagnosed with a respiratory syncytial virus (RSV) infection?

Yes No

12. Which of these medications has your child been prescribed (at home or in the hospital) since discharge (or last interview)? (Select all that apply)

Inhaled bronchodilators Systemic Steroids

Inhaled steroids Pulmonary vasodilators

Diuretics None of the above

See Medications list on last page

13. How many people normally live in your home including your baby (for at least 6 months of the year)? (select one)

2-3 4-6 7-10 >10

13.a. Are there any children < 5 years of age (other than your baby)? (select one)

None 1-2 3-5 6-8 >8

14. Do you currently have any pets? (select all that apply)

None Dog Cat Other fury animal Fish Birds Other

Questionnaire Completed by (staff): _____ Date: _____

Complete at 6 and 12 months ONLY:

15. What type of milk does your child drink?

Breast milk only Breast milk and Formula Formula Only Other No enteral feedings

16. What is the route of feedings? (select one)

100% Nipple (breast or bottle)
 Naso-gastric or Gastric tube (any NG counts as NG or gastrostomy)
 Parenteral (any parenteral counts as parenteral)

17. Was breast milk discontinued since last interview?

 Yes No

17a. If Yes, how old (in months) was the child when breast milk was discontinued?
(approximate corrected age in Months ____ (months))

18. Does your child receive any care outside the home?

 Yes No

18.a. If yes, who provides care? (select all that apply)

Relatives Daycare Friends Other

18.b. Are other children that are not siblings present at outside care site?

Yes No

19. Please describe the situation regarding smoking in your child's home.

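### Part II respiratory morbidity per quarter is collected over windows of unequal length, and the stated analysis has no term for observed time

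*Combined protocol and SAP*

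**What the plan says.** Section 3.2 sets the objective: "To evaluate respiratory morbidity per quarter and compare pulmonary morbidity across groups". Section 7.3 lists two endpoints that depend on it, "Respiratory morbidity per quarter till 12 months corrected age" and "Proportion of subjects with any respiratory resource utilization at 3, 6, 9 and 12 months corrected age"; section 12.2.3 repeats them. NICU length of stay is in the same lists.

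The timing of the calls is in section 10.2.1: "Follow-Up Questionnaires will be completed by telephone with parents at 3, 6, 9, and 12 months corrected age". The list of abbreviations defines corrected age as "Chronological Age - Weeks Premature", so the call dates do not depend on when the infant went home.

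The look-back period is in Appendix II. Item 8, which is limited to respiratory causes, asks "Since discharge (or last interview), has your child been treated in the Emergency Department or by another doctor in the office or clinic"; item 9 asks "Since discharge (or last interview), has your child been admitted to the hospital overnight". Items 6, 7, 10.c, 10.d, 11 and 12 use the same look-back. The opening question of item 10, with 10.a and 10.b, asks about current status. Item 4 allows for an interview that was not held, and item 3 lets the last interview be any earlier one.

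For categorical data, section 12.13 gives a logit model or GEE adjusted for the stratification factors and for multiple births. It gives no rule for unequal or merged windows.

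**The concern.** A per-quarter comparison presumes that each child is observed for about the same time in each quarter. Here the end of the first window is set by corrected age and its start by discharge, which happens after randomization and could be affected by treatment. An arm that goes home sooner has more weeks in which an emergency visit or an admission can occur before the first call. At the same weekly rate it reports more events, so earlier discharge would count against it.

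Missed calls act differently: the skipped quarter has no answer, and the next answer covers both periods. A yes/no answer over a merged period cannot afterwards be divided between the two quarters.

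**Working it through.** **The plan's own figures.** The documents give no rate, power or sample size for these Part II endpoints, so there is no stated figure to reproduce. The primary-endpoint sample size (82 per arm, section 12.3) reproduces from 40% vs 20%, two-sided 0.05 and 80% power, but the point does not depend on it.

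**Inputs.** From the documents: calls at 3, 6, 9 and 12 months corrected age, a look-back to discharge or the last interview, and corrected age counted from term. Assumed, because the documents give no values: discharge PMA, event rate, and an event rate that is constant over time. Three months is 13.04 weeks.

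**Step 1: first window.** Weeks = 40 + 13.04 − discharge PMA.

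| Discharge PMA (assumed) | First window (weeks) | Multiple of a quarter |
|---|---|---|
| 34 | 19.0 | 1.46 |
| 36 | 17.0 | 1.31 |
| 38 | 15.0 | 1.15 |
| 40 | 13.0 | 1.00 |
| 44 | 9.0 | 0.69 |

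With every call completed on time, windows two to four are each 13.04 weeks. For discharge after 40 weeks PMA, the figure is time at home.

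**Step 2: missed calls.** A missed 6- or 9-month call gives 2 × 13.04 = 26.1 weeks, exactly double. A missed 3-month call makes the 6-month window 26.08 + (40 − discharge PMA) weeks: 31.1 for discharge at 35 weeks (2.4 quarters) and 22.1 at 44 weeks (1.7 quarters).

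**Step 3: effect on a yes/no item.** P(any event) = 1 − exp(−rate × weeks), with the rate set so that the risk over 13.04 weeks equals the value in the first column.

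| Assumed risk per quarter | Discharge 36 wk | Discharge 38 wk | Difference (points, before rounding) | Merged two quarters |
|---|---|---|---|---|
| 10% | 12.9% | 11.4% | 1.4 | 19% |
| 20% | 25.3% | 22.7% | 2.6 | 36% |
| 30% | 37.3% | 33.7% | 3.5 | 51% |
| 50% | 59.6% | 55.0% | 4.5 | 75% |

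With discharge at 35 vs 37 weeks (windows of 18 and 16 weeks) and rates of 1%, 2% and 4% per week, the proportions are 16.5% vs 14.8%, 30.2% vs 27.4% and 51.3% vs 47.3%. A one-week difference (37 vs 38 weeks) gives 0.7 to 2.3 points over the 10% to 50% range.

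**Step 4: size against sampling error.** Take 30.2% vs 27.4% with 82 per arm. The standard error is √[(0.302 × 0.698 + 0.274 × 0.726)/82] = 0.071. The gap of 0.028 is 0.4 standard errors, which moves a nominal two-sided 5% error rate to about 6.9%.

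**The case against.** The best defence is that unequal windows bias a randomized comparison only if discharge timing or missed calls differ by arm. The only evidence in the documents is in section 2.2.3.2, where median NICU stay with AeroFact was comparable to historical controls. Those data are small and non-randomized, but nothing in the documents points the other way, and nothing suggests differential missed calls. Even a two-week shift is small against sampling error (step 4). This stands and limits the claim.

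It can also be said that section 12.13 is a generic list by variable type and that section 12 defers detail to a separate SAP. That SAP may deal with observed time; the text reviewed contains no such rule. The form does record the dates needed: last interview (item 2), NICU discharge (2a), which interview was last (3) and the current interview (4.i). So the gap can be closed in the analysis.

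A reader might infer from the N/A option in items 8 and 9 that an infant still in hospital contributes no resource use. The form does not support that. Item 10 asks about oxygen or a ventilator at home or in hospital, item 12 covers drugs prescribed in either place, and item 4.ii allows an inpatient interview. Only outpatient treatment and overnight admission can be marked N/A.

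A reader might also conclude that the look-back should simply become a fixed three months. That would lose the earlier events after a missed call, and it would not equalize time at home after late discharge. The present wording has the merit of complete coverage.

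**Conclusion.** The point holds as a gap in the analysis plan. The first window varies with discharge date, a missed call merges windows, and the stated model has no term for either. If one arm goes home two weeks earlier, its first-quarter proportion rises by roughly 1 to 5 points with no true difference, over assumed quarterly risks of 10% to 50% and a constant rate. If stay and missed calls are alike across arms, the cost is noise and a label that does not match the period covered. The stronger conclusion, that the comparison is biased against AeroFact, is not supported, because the documents show no difference in stay or in missed calls.

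One ambiguity affects late discharges. The synopsis states "Part II will begin at discharge/40 weeks PMA and include telephone Questionnaires", whereas section 4.2 starts Part II at discharge. For an infant in hospital beyond 40 weeks PMA, the start of the first look-back is therefore unclear, and the two statements should be reconciled.

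These are additional Part II endpoints, outside the multiplicity procedure of section 12.11, which covers primary and secondary endpoints only. The change is worth making because it is cheap, but the primary conclusion does not depend on it.

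**What to change.** Keep the Appendix II look-back wording. In the analysis plan for these Part II endpoints:

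- Compute each child's observed time at home in each window from items 2, 2a, 3 and 4.i.
- Analyse the admission counts (9.a and 9b) with a rate model and a log-time-at-home offset.
- Analyse the yes/no items with a complementary log-log model and a log-time offset. Under a constant rate this link matches 1 − exp(−rate × time). Keep the planned adjustment for strata and multiple births. The visit count in 8.a is recorded in bands, so use the yes/no answer to item 8.
- Label any answer after a missed call as covering the merged period, not a single quarter.
- Report the unadjusted proportions alongside, with the distribution of window lengths and missed calls by arm.

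The cost is a little more analysis work and a constant-rate assumption within each window. No new data are needed.

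### Part II item 10 has no field for oxygen or ventilation given during a readmission that ended before the call, or for earlier ventilation in a child now on oxygen

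*Combined protocol and SAP*

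**What the plan says.** Section 10.2.1 sets the timing: "Follow-Up Questionnaires will be completed by telephone with parents at 3, 6, 9, and 12 months corrected age". The schedule tables in section 4.2 and Appendix II list oxygen/ventilator use as a row of its own at all four calls, without restricting it to home. Section 3.2 gives the objective: "To evaluate pulmonary outcomes and respiratory resource utilization at 3, 6, 9, and 12 months corrected age". Section 7.3 lists among the endpoints: "Proportion of subjects with any respiratory resource utilization at 3, 6, 9 and 12 months corrected age".

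The relevant Appendix II items are:

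- **Item 10** asks about the present: "Is your child currently on oxygen or a breathing machine (ventilator) at home (or in hospital". Under Yes stand 10.a and 10.b, which ask whether the child is now on oxygen or on a ventilator.
- **Items 10.c and 10.d** stand under No and look back over the interval, for home use only: "Has your child been on oxygen at home since discharge (or last interview" and "Has your child been on a ventilator at home since discharge (or last interview".
- **Item 9** looks back for admissions: "Since discharge (or last interview), has your child been admitted to the hospital overnight". Items 9.a and 9b count all overnight admissions and those for breathing problems.
- **Item 12** looks back for medication in both settings: "Which of these medications has your child been prescribed (at home or in the hospital) since discharge (or last interview".

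**The concern.** Item 10 mixes two scopes. Its current-status part includes hospital, while its look-back part does not. Whether oxygen or ventilation during a readmission is recorded therefore depends on whether the call happens to fall within the episode. The Yes branch has no look-back at all, so a child on support at the call loses any record of a different or heavier form of support earlier in the interval.

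At stake is the period measure of oxygen/ventilator use: whether it can be read as use since the last contact, and whether it can grade the severity of post-discharge respiratory illness. Analysis of the questionnaire data cannot restore an answer that was never asked for.

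**Working it through.** The plan states no figure on this point, so there is none to reproduce. The check is a reading of the branches, followed by a range calculation on assumed durations.

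**Step 1. Follow the branches.**

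| Course since discharge or last call | Item 10 | Next items | Support recorded |
|---|---|---|---|
| Readmitted and supported, off support by the call, no home support | No | 10.c No, 10.d No | None |
| Same episode, still in progress at the call | Yes | 10.a and/or 10.b Yes | Yes |
| Now on oxygen, ventilated earlier in the interval | Yes | 10.a Yes, 10.b No | Oxygen only |
| Home oxygen that ended before the call, plus ventilation during a readmission | No | 10.c Yes, 10.d No | Home oxygen only |

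The third row needs no assumption about rates or stay lengths. It follows from the layout alone, and holds even if the earlier ventilation was at home.

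**Step 2. Look for another field.** Items 9 to 9b count the admission but not what was given during it. Item 8 covers emergency and clinic treatment, item 11 RSV and item 12 medication. The adverse-event route does not help, because sections 8.2, 8.2.7 and 12.2.4 restrict Part II recording to SAEs that result in death. No field holds non-fatal in-hospital support that ended before the call.

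**Step 3. Range for the share missed.** Inputs:

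- T, the interval between calls: 365.25/4 = 91.3 days, from the quarterly schedule in section 10.2.1.
- L, days of in-hospital support: assumed, since the documents give no readmission rate, stay length or support rate.
- h, the share of such children who also had home support in the interval and so are recorded as users anyway: assumed.

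If the call falls on a random day of the interval, P(captured) = L/T. With no home support the share missed is 1 − L/T.

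| L (days) | L/T | Missed, h = 0 | Missed, h = 0.2 |
|---|---|---|---|
| 3 | 3.3% | 97% | 77% |
| 7 | 7.7% | 92% | 74% |
| 14 | 15.3% | 85% | 68% |
| 30 | 32.9% | 67% | 54% |

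The last column is (1 − h)(1 − L/T). With h = 0, more than half are missed for L up to about 45 days (1 − 45/91.3 = 51%). The share missed falls to one half when h = 1 − 0.5/(1 − L/T), which is 0.48, 0.46, 0.41 and 0.26 for L = 3, 7, 14 and 30.

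The first interval can be longer, because section 10.1.5.2 allows for discharge before 36 weeks PMA. From 36 weeks PMA to 3 months corrected age is about 4 + 13 = 17 weeks, or 119 days. Then 3/119 = 2.5% and 14/119 = 11.8% are captured, and about 88% to 97% are missed.

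**Step 4. After the change.** If 10.c and 10.d covered home and hospital and were asked of everyone, every recalled episode would have a field. The share missed by design would be 0%, leaving only recall error.

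**The case against.** The strongest reply is that item 10 is meant to measure continuing or home support and does so correctly. The hospital wording in its stem has a plausible purpose, namely infants who have not yet gone home. The synopsis starts Part II at discharge or 40 weeks PMA, item 2a allows N/A for NICU discharge, item 4 allows an in-patient interview, and item 26 has an option for infants still in hospital. Section 10.2.1 speaks of current respiratory support. Acute hospital care has its own items, 9 to 9b. On this reading, a No at 10.c from a child treated in hospital is a true answer, and item 12 simply has a different scope for a different topic.

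Much of this stands. The difference from item 12 is not a contradiction, and the form nowhere records an absence of in-hospital use. But 10.c and 10.d ask about the interval, so the item is not purely current status. The stem accepts hospital use, so it is not purely home support either. If home support is all that is wanted, neither the form nor the schedule row says so.

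The skip pattern is read from layout. Items 6.a, 7.a and 8.a carry an explicit if-yes instruction, and 10.a to 10.d do not. The branch is likely rather than certain.

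A reader might infer that the most severe post-discharge respiratory events are lost, or that the utilization comparison is compromised. The documents do not support either. Items 8, 9 to 9b, 11 and 12 still capture the event, and deaths are recorded separately. What is missing is one attribute of an admission already counted. Nor do the documents define the components of the utilization, pulmonary-outcome or morbidity endpoints (section 12 defers detail to a separate SAP), so item 10's role in each is inferred. The wording is the same in all arms, and nothing suggests bias between them.

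**Conclusion.** The point holds as a minor gap in one questionnaire item behind additional endpoints. It does not touch the 7-day primary endpoint, the Part I safety data or the testing order in section 12.11. As laid out, item 10 has no field for in-hospital support that ended before the call in a child never on home support, and none for earlier ventilation in a child now on oxygen.

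A composite of any respiratory utilization that counts breathing-related admissions would be largely unaffected. The loss is confined to oxygen/ventilator use as a separate topic and as a severity measure.

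The size, about 85% to 97% of such episodes missed, rests on three assumptions: supported stays of 3 to 14 days, a call on a random day of a roughly 91-day interval, and no home support. It is a share of episodes whose number the documents do not let us estimate. It should not be read as a share of all oxygen or ventilator use, and it falls as home support becomes more common among readmitted children.

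**What to change.** - Ask 10.c and 10.d of every child, whatever the answer to item 10.
- Extend both to use at home or in hospital over the same look-back period as item 12, excluding the initial NICU stay, with separate boxes for home and hospital.
- Define period use as Yes to any of 10.a to 10.d, and report home use separately. State how infants still in their first admission at the call are handled, since 10.a and 10.b would count them while the reworded look-back would not.
- If the sponsor wants home support only, say so in the item, in the schedule row and in the endpoint definition.

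The cost is a wording and skip-pattern change to one item, and two extra yes/no answers for children on support at the call. No treatment, visit or Part I procedure changes. Interviews already held keep the old wording, so the dataset would contain two versions of the item. Flag the version on each record, and keep home use as the measure common to both where it is available. Under the old form, a Yes at item 10 does not say whether the support was at home or in hospital.
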